## 3. Study Procedures

### 3.1 Study Design

This study will be a prospective randomized control trial. The study will also be double blind, as the patient and physician will not know which injection is being used. Both interventions (Kenalog + Lidocaine with epinephrine and Kenalog alone) can be classified as standard of care, as they are already being used in our clinic and by surgeons around the world in a similar fashion.

Syringes will be pre-filled by the study personnel with either:

1. 1mL 1% lidocaine with epinephrine with epinephrine and 1ml of Kenalog 40 (2 mL total)

2. 1mL of 0.9% saline and 1ml of Kenalog 40 (2 mL total)

Patients will have an equal (50% chance) of receiving either injection that will be determined by using randomizer software.

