### **3.2 Data points**

We will keep track of the following:

- Patient identification (medical record number)
- Age
- Gender
- Type of Injection
- Date of injection
- Digit/Hand
- Reported Pain Score at 1 minute
- Adverse effects of injection (infection, skin pigmentation, atrophy)

We will also be keeping track of the following comorbid conditions to better analyze our data:

- Diabetes (insulin dependent, non-insulin dependent)
- Hypothyroidism
- Chronic opioid use
- Smoking history
- Carpal tunnel syndrome
- Rheumatologic conditions

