### **3.6 Statistical Analysis**

We are planning a study of a continuous response variable from independent control and experimental subjects with 1.1538 control(s) per experimental subject. In a previous study the response within each subject group was normally distributed with standard deviation 0.3. If the true difference in the experimental and control means is 0.2, we will need to study 34 experimental subjects and 39 control subjects to be able to reject the null hypothesis that the population means of the experimental and control groups are equal with probability (power) 0.8. The Type I error probability associated with this test of this null hypothesis is 0.05.

Demographic data and adverse events will be assessed with the chi-square analysis.

Pain scores will be assessed with the Manny-Whitney U test.

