## **4. Adverse Reporting**

Adverse events will be reported to the IRB immediately through standard reporting mechanisms. The attending surgeon will be involved with the post-care along with any necessary physician staff.

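### Does the lack of a stated window or method for finding adverse events undermine their chi-square comparison?

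*Combined protocol and SAP*

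**What the plan says.** Section 3.6 gives the analysis: "Demographic data and adverse events will be assessed with the chi-square analysis". Section 3.2 names the events: "Adverse effects of injection (infection, skin pigmentation, atrophy". In the same list the one timed outcome is "Reported Pain Score at 1 minute" and the one date is "Date of injection". The list also holds the medical record number, which Section 5 confirms as the patient identifier, and Section 6 places the study at one clinic.

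Section 4 covers reporting, "Adverse events will be reported to the IRB immediately through standard reporting mechanisms", and care after the injection: "The attending surgeon will be involved with the post-care along with any necessary physician staff". It sets no visit, window or check. On masking, Section 3.1 says: "The study will also be double blind, as the patient and physician will not know which injection is being used". For size, Section 3.6 says "we will need to study 34 experimental subjects and 39 control subjects", which is 73 in all. That figure is for the pain comparison; no event rate or difference in event rates is given anywhere.

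**The concern.** A chi-square table needs a count of patients without the event as well as with it. The listed events would not be expected to show at the only scheduled assessment, 1 minute after injection, so the information has to come from somewhere the plan does not describe. On the listed items alone, a patient who was checked and clear looks the same as one who was never checked, unless the adverse-effect item allows for not assessed.

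If unchecked patients entered the table as event-free, recorded rates would be too low in both arms, the test would lose power, and a low or zero count might be taken as evidence of safety.

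**Working it through.** **The plan's own figure.** Inputs from Section 3.6: difference 0.2, SD 0.3, 34 and 39 patients, alpha 0.05 (taken as two-sided). The noncentrality is 0.2 / (0.3 × √(1/34 + 1/39)) = 2.84. With 71 degrees of freedom, noncentral t power is 0.800, as stated. There is no corresponding figure for adverse events, so every rate below is an assumption.

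**If unchecked patients are counted event-free.** Let p be the true event rate and r the fraction checked, equal in both arms and unrelated to the event. The recorded rate is p × r, and the chance of no recorded event is (1 − p × r)^73. Power is by full enumeration of the tables at 34/39 with the uncorrected Pearson test at 0.05, counting tables with no events as non-rejection. Ranges show which arm has the higher rate.

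| r | Recorded rate, p = 5% | Chance of zero in 73 | Power, 5% v 25% | Power, 5% v 20% | Type I error, common 5% |
|---|---|---|---|---|---|
| 1 | 5% | 2.4% | 70-72% | 50-52% | 2.3% |
| 0.9 | 4.5% | 3.5% | 64-66% | 45-47% | 1.9% |
| 0.5 | 2.5% | 16% | 32-35% | 18-22% | 0.5% |
| 0.3 | 1.5% | 33% | 11-15% | 5-9% | 0.1% |

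Under equal checking the damage is understatement and lost power. The false-positive rate falls rather than rises.

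**What complete checking would deliver.** Both arms receive the same 1 mL of Kenalog 40 (Section 3.1), and nothing in the documents suggests a 15 to 20 point difference. With r = 1, power is 28-30% for 5% v 15% and 10-11% for 5% v 10%. The chance of zero events is 0.98^73 = 23% at a true 2% and 0.99^73 = 48% at a true 1%. For differences and rates of that order, 73 patients say little however well they are followed.

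**Testing checked patients only.** The natural remedy is to leave unchecked patients out of the chi-square denominator.

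- *Checking unrelated to the event.* For 5% v 25%, power at r = 0.5 is 37-41% instead of 32-35%, and at r = 0.3 it is 18-23% instead of 11-15%. The gain is modest.
- *Patients with events checked more often (90% v 50%).* Over all patients, a true 5% is recorded as 0.05 × 0.9 = 4.5%. Over checked patients it becomes 0.045 / (0.045 + 0.95 × 0.5) = 0.045 / 0.52 = 8.7%. Power for 5% v 25% is 64-66% over all patients and 59-62% over checked patients.

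The second pattern is plausible where patients return because something is wrong. There the remedy loses power and moves the recorded rate further from the truth. It also bases the test on a subset formed after randomisation.

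**The case for a change.** The strongest case for a change is that this is a planned test whose denominator is not defined. Section 4 says where events are reported but not how they are found. Adding a checked yes/no item and a last-contact date for about 73 patients is cheap, whereas follow-up status not recorded during the trial may be hard to reconstruct. Showing rates over both denominators would bracket the true rate whenever patients with events are at least as likely to be checked.

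The description of the gap stands: no visible text gives a window or method. A contact described only in the consent pages, which are not in the available text, could not be seen.

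The need for an amendment does not follow. The harm requires unchecked patients to be coded event-free, a rule the plan does not state; whether an item allows for not assessed is a matter for the case report form. The medical record number and injection date let the team look up later entries for each patient, which is the same source a record-review remedy would use. Such a look-up shows how many patients have no later entry but cannot recover their outcomes, whether or not the protocol is amended. The proposed text would also leave the window and method for the investigators to fill in, so it would not itself settle what is missing.

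**Conclusion.** The concern describes a real omission but does not warrant a change. It is missing operational detail of a kind a competent team fills when it builds the form and writes the report, by saying how events were found and for how many patients no later information exists. The objective in Section 2 concerns pain and effectiveness; there is no safety hypothesis that a low event count could wrongly confirm. Randomisation and blinding make unequal checking between the arms unlikely.

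The possible size depends on assumptions throughout. At an assumed 5% rate with half the patients checked at random and the rest counted clear, the recorded rate is halved and the chance of a zero count is 16% instead of 2.4%. If patients with events are the ones more often seen, at 90% v 50%, the recorded rate is 4.5% and little is lost. The one concrete change to the analysis, a chi-square over checked patients only, gains some power in the first case and loses some in the second, so the test over all randomised patients is a fair choice to leave in place.

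### Section 3.6 states power of 0.80 for a t-test on means, but the Mann-Whitney test it names for pain has about 0.78 on the same inputs: a minor mismatch, mended by restating the power

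*Combined protocol and SAP*

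**What the plan says.** Section 3.6 (Statistical Analysis) holds both the sample size statement and the choice of test.

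- **Sizing.** The response in each group is taken as "normally distributed with standard deviation 0.3". The effect is given by "If the true difference in the experimental and control means is 0.2". The 34 experimental and 39 control patients are said to be enough to "reject the null hypothesis that the population means of the experimental and control groups are equal with probability (power) 0.8". The error rate follows: "The Type I error probability associated with this test of this null hypothesis is 0.05".
- **Analysis.** Shortly afterwards: "Pain scores will be assessed with the Manny-Whitney U test" (a misprint for Mann-Whitney).

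Nothing connects the two. The section gives no power for a rank test and no allowance for its efficiency, and it does not say that the calculation on means is meant as an approximation. It does not state whether the test is one-sided or two-sided.

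**The concern.** A null hypothesis of equal means with normal responses describes a two-sample t-test. The Mann-Whitney test is slightly less efficient than the t-test when the data really are normal, so the stated power may not be that of the planned analysis. The calculation leaves no room to absorb a loss: at 34 + 39 the t-test only just reaches 0.80, and no dropout allowance is stated.

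What is at stake is modest. This is the only power figure in the plan, and it describes a test that the plan does not name for pain. Someone who relies on it would take the chance of missing a true difference of 0.2 as 20%, when on the plan's own assumptions it is about 22%.

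**Working it through.** **Inputs, all from section 3.6:** n = 34 and 39; difference 0.2; SD 0.3; normal responses; alpha 0.05. Standardised difference: 0.2 / 0.3 = 0.667. Two-sided testing is an assumption, checked in step 1. The power sentence does not name its response variable. I take it to be the pain score, the only outcome score listed in section 3.2.

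**Step 1: reproduce the stated 0.80 (two-sample t-test).**
- Noncentrality = 0.667 / √(1/34 + 1/39) = 0.6667 / 0.2346 = 2.841.
- Degrees of freedom = 34 + 39 − 2 = 71; two-sided 5% critical value 1.994.
- Power from the noncentral t = **0.8003**, which matches the plan.
- The two-sided normal approximation gives Φ(2.841 − 1.960) = 0.811. A one-sided test by the same approximation gives 0.884, so the two-sided t-test is the reading that fits.

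**Step 2: Mann-Whitney power on the same inputs.**
- *Efficiency adjustment.* Under normality the asymptotic efficiency of Mann-Whitney relative to the t-test is 3/π = 0.955. Effective sizes are 34 × 0.955 = 32.5 and 39 × 0.955 = 37.2. The noncentrality becomes 2.841 × √0.955 = 2.777, and the power is **0.781**.
- *Simulation.* 200,000 trials of 34 + 39 with normal responses, SD 0.3 and shift 0.2, using the normal approximation to U, give **0.781**. Repeat runs gave 0.779 to 0.780.
- *Noether's formula* (a rougher approximation). P(one response exceeds the other) = Φ(0.667/√2) = 0.681; the fraction in one group is c = 34/73 = 0.466. Power = Φ(√(73 × 12 × 0.466 × 0.534) × 0.181 − 1.960) = Φ(0.717) = 0.763.

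All three fall below 0.80. Simulation and the efficiency adjustment agree on about 0.78.

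**Step 3: size at which Mann-Whitney reaches 0.80.**
- Dividing by the efficiency: 34 / 0.955 = 35.6 and 39 / 0.955 = 40.8, so 36 + 41 = 77.
- Simulation at 36 + 41: 0.803, or 0.800 with continuity correction.
- Noether's formula gives about 80 in total.
- Against 73, the increase to 77 is 4 patients, or 4/73 = 5%.

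**Step 4: other checks.**
- Simulated type I error of Mann-Whitney at 34 + 39 is 0.049, so alpha holds.
- With a nearly equal split of 36 + 37, the t-test has power 0.802 and Mann-Whitney 0.778 to 0.783. The gap does not come from the unequal split.

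**Step 5: how far the result depends on the inputs.**
- *Precision of the SD.* t-test power at 34 + 39 is 0.826 for SD 0.29, 0.782 for SD 0.307 and 0.774 for SD 0.31.
- *Shape of the scores.* The shapes below are assumed, because the documents give no pain distribution. Each keeps SD 0.3, shift 0.2 and 34 + 39 (50,000 runs each):

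| Shape | Mann-Whitney | t-test |
|---|---|---|
| Normal (200,000 runs) | 0.781 | 0.802 (exact 0.800) |
| Logistic | 0.825 | 0.800 |
| t with 5 df | 0.864 | 0.802 |
| Laplace | 0.900 | 0.801 |
| Gamma, shape 4 | 0.843 | 0.799 |
| Uniform | 0.745 | 0.801 |

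- *Ties.* If the score were whole points from 0 to 10 with SD 3 and difference 2 (also an assumption), Mann-Whitney power is about 0.77 to 0.78.

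**The case against.** The strongest reply is that nothing is miscalculated and the gap is too small to matter. Section 3.6 attaches its 0.80 to a test of equal means, and for that test the figure is right. Sizing on means and then analysing a VAS score by ranks is a familiar simplification. The shortfall is about 2 points, and an SD of 0.307, which rounds to the stated 0.3, would by itself take the t-test to 0.782. The direction is not fixed either: with heavier tails or skewness Mann-Whitney gains power, and with a flat distribution it loses more.

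Most of this stands. It rules out three stronger readings that a reader might infer:

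- **That the sample size contains an arithmetic error.** It does not; 0.80 reproduces as 0.8003.
- **That the trial is materially underpowered, or should enrol more.** A 2-point gap that holds only under exact normality does not support that.
- **That the t-test should become the primary analysis.** The t-test would match the calculation, but for a VAS score the choice is a trade-off. Mann-Whitney does better in four of the five non-normal shapes tried, and the documents give no data to settle it.

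What the reply does not remove is the mismatch itself. The plan asserts normality, and under that assertion the named test does not have the stated power. If the sponsor doubts normality, the 0.80 loses its stated basis as well. Either way the sentence needs its condition and its test spelled out.

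**Conclusion.** The point holds as a minor mismatch between the sizing test and the analysis test. On the plan's own assumptions the planned test misses its stated power by about 2 points. This rests on normal, untied responses, two-sided testing, and reading the power sentence as referring to pain. It is a matter of stating the power accurately; the validity of the analysis is not in doubt.

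A reader might also infer that this affects the trial's only efficacy question. The documents do not support that. They designate no primary outcome, and the Abstract and section 2 raise effectiveness of treatment as well as injection pain.

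**What to change.** Keep the enrolment and the Mann-Whitney test. Replace the power sentence in section 3.6 with wording such as:

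> Under normally distributed responses with SD 0.3 and a true difference of 0.2, 34 and 39 patients give the Mann-Whitney test power of about 0.78 at two-sided 0.05 (0.80 for a t-test on means); power may be higher or lower if scores are not normal or are tied.

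Two decimals are enough, given an SD quoted to one digit. The misprinted test name can be corrected in the same edit.

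**Cost:** one sentence and no extra patients. **Downside:** the power on record becomes about 2 points less favourable.

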### **3.7 Withdrawal of Subjects**

There are no anticipated circumstances under which subjects would be withdrawn from research without their consent. If subjects withdraw, there will be no penalty or consequences.

## **4. Adverse Reporting**

Adverse events will be reported to the IRB immediately through standard reporting mechanisms. The attending surgeon will be involved with the post-care along with any necessary physician staff.

## 5. Privacy and Confidentiality

Private health information (PHI) will be used in the study, but not disclosed. All PHI will be stored on a secure, password-locked server. All participants in the study have obtained Human Research certification to have the necessary authorization to PHI. When collecting patient data, only medical record numbers will be used to identify patients.

## 6. Communication Plan

Reporting will occur through standard process for the IRB. There is one clinic at a single site performing this study.

## 8. Appendix

|           |  |
|-----------|--|
| Grade I   | Pain/history of catching                                 |
| Grade II  | Demonstrable catching, but can actively extend the digit |
| Grade III | Demonstrable locking, requiring passive extension        |
| Grade IV  | Fixed flexion contracture                                |

### Appendix Item 1: Green's Classification of Trigger Finger Severity

### Appendix Item 2: VAS Pain Score
